- Treatment adherence questions, based on modified versions of the Multiple Sclerosis Treatment Adherence Questionnaire (MS-TAQ); data to be collected via ePRO at baseline (modified for once or twice daily oral dosing to assess adherence during last previous oral DMD treatment or modified for infusion dosing to assess adherence to last previous infusion DMD treatment) and at the end of Months 1, 2, 13, and 14 (modified for cladribine tablets); a Spanish translation is available to patients.
- Proportion of patients experiencing a relapse. For this study, a relapse will be defined as determined and recorded by the investigator and information on the definition used by the investigator will be collected (see Section 9.1.2.1 for a guide on definition).
- Proportion of patients with relapse associated with hospitalization (relapse as primary diagnosis or reason for hospitalization). For this study, a relapse will be defined as determined by the investigator (see Section 9.1.2.1 for a guide on definition).
- Proportion of patients with relapse associated with glucocorticoid use. For this study, a relapse will be defined as determined by the investigator (see Section 9.1.2.1 for a guide on definition).
- Assessment of previous treatment for MS:
 - Previous DMD(s) received for MS prior to study enrollment, since MS diagnosis
 - Reasons for discontinuation of previous DMD(s)
- Assessment of clinical and demographic characteristics of patients who switch from ocrelizumab to oral cladribine tablets
 - Reasons for discontinuation of ocrelizumab
- Proportion of patients who discontinue oral cladribine tablets
 - Reason for discontinuation of cladribine tablets
 - Elapsed time to discontinuation after first dose
 - Number of doses and % of planned doses (as per USPI) received
 - Subsequent treatment chosen following discontinuation of cladribine tablets
- Assessment of concomitant MS medications used during study period
- The ARR based on the last 24 months (or since MS diagnosis, if diagnosis <24 months) prior to the start of treatment with cladribine tablets (retrospective data). For this study, a relapse will be defined as determined by the investigator (see Section 9.1.2.1 for a guide on definition).

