9.2.2 Definition of Study Cohorts and Description of Treatments

The study will have a single primary cohort that consists of all patients enrolled in the study who received at least 1 dose of cladribine tablets. Additionally, a sub-cohort of approximately 100 patients that directly switched from ocrelizumab to cladribine tablets will be prospectively enrolled. All treatment and other medical decisions will be made by the investigator, with no directives mandated by this study protocol.

All study patients are anticipated to receive marketed cladribine tablets as per investigator discretion and as per US approved label: 3.5 mg/kg body weight over 2 years, administered as 1 treatment course of 1.75 mg/kg per year. Each treatment course consists of 2 treatment weeks, 1 at the beginning of the first month and 1 at the beginning of the second month of the respective year. Each treatment week consists of 4 or 5 days on which a patient receives 10 mg or 20 mg (1 or 2 tablets) as a single daily dose, depending on body weight. Since prescribing is determined by the investigator as per standard of care and according to the USPI, the benefits and risks to patients in being in the study are not different than the benefits and risks to patients taking cladribine tablets as per standard of care and according to the USPI in the general population.

Following completion of the 2 treatment courses, do not administer additional cladribine tablet treatment during the next 2 years, as stated in the USPI.

As per USPI, ALC values need to be normal at the initiation of cladribine tablets in Year 1, and ALC results need to indicate ≥ 800 cells per microliter at the start of the Year 2 treatment course. If necessary, the Year 2 treatment course should be delayed for up to 6 months to allow for recovery of lymphocytes to ≥ 800 cells per microliter. If this recovery takes more than 6 months, the patient should not receive further treatment with cladribine tablets.

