Other relapse analyses	Proportion of patients experiencing a relapse (24-month and 12-month periods) and ARR over the 12-month period  Proportion of patients with relapse associated with hospitalization and ARR associated with hospitalization  Proportion of patients with relapse associated with glucocorticoid use and ARR associated with glucocorticoid use	24-month treatment period (or 30 months if Year 2 treatment is delayed) and 12-month treatment periods from first dose of cladribine tablets	Section 14.2
To assess treatment patterns (Multiple Sclerosis [MS] treatment prior to transition to cladribine tablets since MS diagnosis, concomitant treatment for MS during the last 2 years prior to initiation of cladribine tablets [or since MS diagnosis if diagnosis <24 months], follow-up treatment in case of discontinuation of cladribine tablets), and, in particular, to assess the clinical and demographic characteristics related to the sequential use of ocrelizumab to cladribine	Assessment of previous treatment for MS: 
 
Previous DMDs received for MS during the last 2 years
 
Number of previous DMDs received for MS (a) during the last 2 years and (b) in total
 
Reasons for discontinuation of last previous DMD
 
 Assessment of concomitant MS medications used during the study period  Proportion of patients who discontinue cladribine tablets: 
 
Reason for discontinuation of cladribine tablets
 
Elapsed time to discontinuation after the first dose of cladribine tablets
 
Number of doses and % of planned doses of cladribine tablets (as per United States Product Information [USPI]) received
 
	For previous treatment: 24-month period prior to initiation of cladribine tablets  For concomitant medication, cladribine tablets discontinuation and subsequent treatment: 24-month period from first dose of cladribine tablets (or 30 months if Year 2 treatment is delayed)	Section 11.3, 12 and Section 13

Objectives	Endpoints (Outcome Measures)	Endpoints (Outcome Measures) Timeframe	IAP Section
	
Subsequent treatment chosen following discontinuation of cladribine tablets
 
Assessment of clinical and demographic characteristics of patients who transition from ocrelizumab to oral cladribine tablets:
 

• Reasons for discontinuation of ocrelizumab

		

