### **Time-to-Event Data**

Time-to-event data will be summarized descriptively as continuous data and using Kaplan-Meier (KM) analysis. Data summarization will include:

- Plot of the KM curve with the number of patients at risk

- KM estimates with CI at fixed timepoints (e.g., every 6 months) (with number at risk/failed)
- Median survival times with CI, and the first quartile (Q1) and third quartile (Q3).

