The number and percentage of patients who started other MS treatments after discontinuation of cladribine tablets will be reported (using the number of patients who discontinue cladribine tablets as the denominator).

Reasons for discontinuation of cladribine tablets will be collected, and, for each reason, the corresponding number and percentage of patients will be reported (using the number of patients who discontinue cladribine tablets as the denominator).

A listing of concomitant MS medications started after discontinuation of cladribine tablets will be provided. The following variables will be reported:

- Patient ID
- Medication name
- Visit
- Dose
- Unit
- Frequency
- Route of administration
- Start date / ongoing (Yes/No) / stop date
- Last study treatment administration date

The elapsed time to discontinuation of cladribine tablets will be calculated as follows:

*Elapsed time to discontinuation of cladribine tablets = Date of discontinuation of cladribine tablets – Date of first study dose*

It will be summarized as a continuous variable and also reported through KM analysis. The ‘Last study treatment administration date’ according to the treatment termination form will be used as the date of discontinuation of cladribine tablets both for patients discontinuing the treatment early and for patients who complete treatment (for patients completing treatment, this will be a censoring date).

The number of doses and % of planned doses (as per USPI) received will be summarized descriptively.

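### SAP 13 censors patients who complete both courses at their last tablet, so the Kaplan-Meier discontinuation curve over-weights any stop after about Month 13 and cannot reach Month 24

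*SAP*

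**What the plan says.** Protocol 9.1.2.2 lists "Elapsed time to discontinuation after first dose" as a sub-item of the proportion of patients who discontinue cladribine tablets.

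SAP 13 defines the elapsed time as the date of discontinuation minus the date of first dose. It takes the last administration date on the treatment termination form as that date "both for patients discontinuing the treatment early and for patients who complete treatment", and adds in parentheses that "for patients completing treatment, this will be a censoring date". Of the resulting variable it says "It will be summarized as a continuous variable and also reported through KM analysis", without naming a narrower population for the continuous summary.

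SAP 9 (Time-to-Event Data) plans "KM estimates with CI at fixed timepoints (e.g., every 6 months) (with number at risk/failed". SAP 5 sets the timeframe for discontinuation as "24-month period from first dose of cladribine tablets (or 30 months if Year 2 treatment is delayed". Neither section treats completion of both courses as a competing event.

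SAP 13 also reports the number and percentage of patients who discontinue, with reasons. SAP 10.1 repeats the count under disposition.

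**The concern.** Censoring at a given time assumes that the patient could still have the event afterwards, at the same rate as those who remain at risk. A patient who has finished both courses cannot, because no further tablets are planned in the study. Protocol 9.2.3 keeps such patients under observation, so it is known that they did not discontinue.

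Censoring them at the last tablet has two effects on the curve. The risk set collapses once most patients finish Year 2, and any later stop is divided by the few who started Year 2 late. The curve also ends before the endpoint's own timeframe does. Separately, a completer who is given a discontinuation date can enter the mean and median time to discontinuation. Those figures would then describe the dosing calendar. The study report could carry a KM figure that disagrees with the crude percentage from the same section.

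**Working it through.** The documents state no discontinuation rate or KM value, and the SAP's precision table is redacted, so there is no plan figure to reproduce. The dates come from the documents. The rates and sample size below are assumptions.

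**Step 1: last-tablet dates.** Protocol 9.2.2 places the treatment weeks "1 at the beginning of the first month and 1 at the beginning of the second month of the respective year", with 4 or 5 dosing days each (5 used), and allows a Year 2 delay of up to 6 months. SAP 9 sets 1 month = 30.4375 days. The fifth dosing day is 4 days after the start of the week.

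| Patient | Days from first dose | Months |
|---|---|---|
| Year 1, week 1 only | 4 | 0.13 |
| Full Year 1, no Year 2 | 30.4375 + 4 = 34.4 | 1.13 |
| Stops after Year 2 week 1, no delay | 12 × 30.4375 + 4 = 369.3 | 12.13 |
| Completer, no delay | 13 × 30.4375 + 4 = 399.7 | 13.13 |
| Stops after Year 2 week 1, 6-month delay | 18 × 30.4375 + 4 = 551.9 | 18.13 |
| Completer, 6-month delay | 19 × 30.4375 + 4 = 582.3 | 19.13 |

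No time exceeds about 19.1 months, so the number at risk at Month 24 is 0 whatever the rates are.

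**Step 2: direction of the error.** Patients who never start Year 2 are dated at about Month 1, before any completer is censored. With no other censoring, KM therefore equals the crude proportion up to about Month 13. For a later event, KM multiplies survival by 1 − 1/n, where n counts only patients not yet censored. The right denominator also includes event-free completers and so is at least n. KM can be too high but never too low.

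**Step 3: worked example (assumed, N = 200).** Four patients stop after Year 1 week 1, 36 after the full Year 1 course, and 2 after an undelayed Year 2 week 1. Another 128 complete without delay. The remaining 30 start Year 2 late, with delays spread evenly from 0.5 to 6 months. After Month 13.1 survival is 158/200 = 0.79, and 30 patients remain at risk.

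| Stops among the 30 delayed patients | KM survival under SAP 13 | KM discontinued | Crude |
|---|---|---|---|
| None | 0.79 | 21.0% | 42/200 = 21.0% |
| One, with 20 at risk | 0.79 × 19/20 | 25.0% | 43/200 = 21.5% |
| One, with 6 at risk | 0.79 × 5/6 | 34.2% | 21.5% |
| Three, with 25, 19 and 7 at risk | 0.79 × 24/25 × 18/19 × 6/7 | 38.4% | 45/200 = 22.5% |

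The crude column is also what cumulative incidence gives, with completion as a competing event. One late stop adds 0.5 points to the crude figure but 4.0 to 13.2 points to KM.

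**Step 4: average size (assumed rates).** The simulation used 1,500 cohorts of 200, with 15% stopping in Year 1. Year 2 started between Months 12 and 13, and 20% of patients were delayed a further 1 to 5 months. There was no other censoring.

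| Year 2 starters stopping mid-course | Mean excess of KM over crude | Cohorts with excess above 2 points |
|---|---|---|
| 0% | 0 points | none |
| 1% | 1.2 | 22% |
| 2% | 2.5 | 42% |
| 5% | 5.7 (24.9% against 19.2%) | 73% |

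Repeat runs move the means by a few tenths of a point. At 1% and 2% the median excess is near 0, so the mean is driven by a minority of cohorts with one late event. At 5% the KM estimate has a standard deviation of 6.5 points, against 2.7 for the crude proportion. About 3 to 7 of 200 patients are at risk at Month 18.

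**Step 5: continuous summary, read literally.** In the first row of the Step 3 example, all 200 patients give a mean of 11.2 and a median of 13.1 months. The 42 who discontinued give a mean of (4 × 0.13 + 36 × 1.13 + 2 × 12.13)/42 = 1.6 and a median of 1.1 months. The all-patient median sits at the end of the second course because 79% of the values belong to completers.

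**The case against.** A reader might infer that KM is simply too high after Month 13. The documents do not support that. The curve stays at the correct level unless a patient who started Year 2 late stops within that course. With no such patient the error is zero, and Months 6 and 12 are unaffected in any case. No stop rate or delay rate is given, so no single excess can be called the effect of the rule. This part of the objection stands, and the point is worded accordingly.

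A reader might also infer that the reported proportion discontinuing is wrong. It is not: the counts in SAP 13 and SAP 10.1 do not use the censoring rule. The curve is descriptive and no decision depends on it.

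On Month 24, the six-monthly spacing in SAP 9 is only an example, numbers at risk are shown, and a statistic that cannot be calculated is printed as such. The result would be an empty cell, not a false number. That is true. The endpoint's timeframe is nevertheless 24 or 30 months, and the data to fill that cell are being collected.

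On the continuous summary, the protocol places elapsed time under patients who discontinue, and a censoring date has meaning only for KM. The intended population is probably the discontinuers, and the documents do not show a deliberate plan to pool completers. The SAP sentence still permits it, so the wording needs settling.

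**Conclusion.** The point holds as a minor correction to a descriptive secondary outcome.

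Three parts rest on the documents alone. Completers are censored at their last tablet although they can no longer discontinue and are still followed. Nobody is at risk at Month 24 on the stated schedule. The continuous summary is not limited to patients who discontinued.

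The upward error in KM is conditional. It is zero without mid-course stops among late Year 2 starters. Under the assumed rates it averages about 1 point at 1% mid-course stops, 2.5 at 2% and 6 at 5%, with wide variation between cohorts. These sizes assume 200 patients, 15% Year 1 stops, 20% delayed and no loss to follow-up. The direction, never below the crude proportion, does not depend on the rates but does assume no other censoring.

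**What to change.** In SAP 13, replace the parenthesis on completers. Treat completion of both planned courses as a competing event and report the cumulative incidence of discontinuation to Month 24 (Month 30 where Year 2 is delayed). Keeping completers event-free to the end of their observation period gives the same estimate when they are followed throughout. Cumulative incidence is the better lead because it does not list patients who have finished treatment as still at risk of stopping it.

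Add that the continuous summary of elapsed time covers only patients who discontinued, as the protocol's outcome list implies.

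The cost is one or two SAP sentences and a changed status variable. No new data are needed.

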## **14                    Efficacy Analyses**

### **14.1                Primary Endpoint: ARR**

#### **14.1.1            Primary Objective: Analysis of the ARR**

Analysis (Analysis Population)	Derivation	Statistical Analysis Methods	Missing Data Handling
Primary endpoint: ARR over 24 Months			
Primary (FAS)	
ARR over 24 months. The ARR over 24 months of a patient is calculated as the number of relapses of the patient, divided by the number of days on study for that patient and multiplied by 365.25. This variable will be considered to get population estimates.
 
A relapse will be defined as per routine clinical practice, as determined by the Investigator.
 
Time on study (days) = (Date of study completion or date of study discontinuation - date of first dose of cladribine tablets + 1)
	
The population estimate will be based on the average of the ARR values for the patients in the study. The corresponding 95% CI will be reported. The Statistical Analysis System (SAS)® MEANS procedure will be used to compute these quantities. The following descriptive statistics will be reported: mean, SD, min, max, median, first quartile (Q1), and third quartile (Q3).
	
Patients discontinuing early are analyzed according to the number of years of follow-up on treatment and the number of relapses observed up to the time of discontinuation.

Secondary (PP)			
Sensitivity (FAS)	
Model-based ARR, defined as expectation of relapses divided by time on study.
	
The estimate of the expected ARR at Month 24 will be based on a negative binomial (NB) model for relapse count, with offset equal to the log of years on study and adjustment for categorical number of relapses in the last 2 years, or since MS diagnosis if diagnosis <24 months (<math>\leq 1</math> relapse, <math>>1</math> relapse). NB regression will be computed with the SAS® Generalized Linear Model (GENMOD) procedure, using the dist=NB option in the MODEL statement.
 
*The estimate of the expected ARR at Month 24 will be based on a zero-inflated NB model for relapse count, with the offset equal to the log of years on study and adjustment for categorical number of relapses in the last 2 years, or since MS diagnosis if diagnosis <24 months (<math>\leq 1</math> relapse, <math>>1</math> relapse). NB regression will be computed with the SAS® GENMOD procedure, using the dist=ZINB option in the MODEL statement.
	
Same handling as for the primary analysis.

Analysis (Analysis Population)	Derivation	Statistical Analysis Methods	Missing Data Handling
Sensitivity (FAS)	
ARR over 24 months considering all reported relapse data. For a patient, such ARR is calculated as the total number of reported relapses in the 24 months after treatment divided by the days on study corresponding to relapse information and multiplied by 365.25.
 
Time on study with relapse information (days) = it is the time on study bounded by 366.25 for patients with relapse information only for the first year; it is the time on study bounded by 731.5 for patients with relapse information in the first year and in the second year.
	
The population estimate will be based on the average of ARR values for the patients in the study. The corresponding 95% CI will be reported. The Statistical Analysis System (SAS)® MEANS procedure will be used to compute these quantities. The following descriptive statistics will be reported: mean, SD, min, max, median, first quartile (Q1), and third quartile (Q3).
	
Patients discontinuing early are analyzed according to number of years of follow-up on treatment and number of relapses observed up to the time of discontinuation.

Sensitivity (FAS)	
Model-based ARR, defined as expectation of reported relapses divided by time on study with relapse information.
	
The estimate of the expected ARR at Month 24 using the definition considering all the reported relapse data will be based on NB model for relapse count using the total number of reported relapses in the 24 months after treatment, with the offset equal to the log of years on study with relapse information and adjustment for categorical number of relapses in the last 2 years, or since MS diagnosis if diagnosis <24 months (<math>\leq 1</math> relapse, <math>>1</math> relapse).
 
NB regression will be computed with the SAS® GENMOD procedure, using the dist=NB option in the MODEL statement.
	
Patients discontinuing early are analyzed according to the number of years of follow-up on treatment and the number of relapses observed up to the time of discontinuation.

ARR: annualized relapse rate; CI: confidence interval; FAS: Full Analysis Set; GENMOD: generalized linear model; NB: negative binomial; PP: per protocol; SAS: Statistical Analysis System; SD: standard deviation.

\* The sensitivity analysis with the zero-inflated binomial model will be considered only if the number of patients without relapses is greater than 5%. Goodness of fit: Standardized deviance residuals will be plotted against the linear predictor to assess the goodness of fit of the model.

The primary endpoint is derived from the number of relapses collected through the eCRF forms “MS Relapse Report” and “MS Relapse Report Details.” A patient will have 0 relapses (at Visit 3 and/or Visit 6) if they reply “No” to the leading question, “Has patient experienced a new MS relapse since last scheduled or unscheduled visit? (Yes, No).” For patient replies of “Yes,” the

number of relapses will be derived from the records in the “MS Relapse Report Details” form. If at Visit 3, the answer to the leading question is not collected, the number of relapses in the first year and the total number of relapses during the second year will be missing. If at Visit 6, the answer to the leading question is not collected, the number of relapses during the second year will be missing.

For ongoing patients during the study, the time on study will take into account the patient’s last available date. This will be used in the interim analyses for all ARR evaluations (primary objective, sensitivity analyses, and secondary analyses).

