9.2.3 Observation Period

Each patient will be followed from the date of first dose of cladribine tablets until loss to follow-up, withdrawal of consent, death, or the end of the data collection period, whichever comes first. Patients will be followed for 24 months from first dose and up to 30 months for those patients who may require a delay of initiation of Year 2 treatment for up to 6 months due to low lymphocyte counts. Follow-up will continue regardless of cladribine tablets discontinuation.

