### **Significance Level**

When CIs are to be calculated, these will be two-sided, with a confidence probability of 95%, unless otherwise specified in this IAP. For continuous data, CIs for the mean will be calculated assuming a normal distribution of the data. CIs for binary endpoints will be presented using the Clopper-Pearson method. All statistical tests mentioned in this IAP are to be regarded as exploratory. The significance level is 5% two-sided. If p-values are to be presented for descriptive purposes, it will be indicated with the statement that no inferential conclusion should be drawn from the p-value.

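### The primary ARR is an unweighted mean of per-patient rates with no minimum follow-up, and the SAP's rules conflict on whether early leavers enter it; an exposure-weighted rate and one consistent rule are needed

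*SAP*

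**What the plan says.** SAP 14.1.1 builds the primary estimate in two steps. Each patient's relapse count is "divided by the number of days on study for that patient and multiplied by 365.25", with time on study equal to "Date of study completion or date of study discontinuation - date of first dose of cladribine tablets + 1". Then: "The population estimate will be based on the average of the ARR values for the patients in the study". PROC MEANS supplies the mean and its 95% CI. SAP section 9 (Significance Level) gives the interval method: "For continuous data, CIs for the mean will be calculated assuming a normal distribution of the data". The full analysis set requires one dose only, and no minimum follow-up is stated. The missing-data column of the same table keeps early discontinuers, with their observed relapses and observed time.

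The text below that table, and SAP 14.1.4, say something different. If the relapse question is not collected at Visit 3 (Month 12), both years' counts are missing. If it is not collected at Visit 6 (Month 24), the Year 2 count is missing. A missing Month 24 count makes that patient's ARR missing, and multiple imputation is only to be considered when more than 5% are missing. SAP 14.1.2 presents the use of Year 1 relapses when Year 2 is missing as an additional sensitivity definition.

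The planned sensitivity analyses include a "negative binomial (NB) model for relapse count, with offset equal to the log of years on study". SAP 14.1.2 reports it by prior-relapse stratum (at most 1, more than 1), with no overall rate specified. Protocol 9.7.3 asks for the ARR with a 95% CI as primary and labels the negative binomial model a sensitivity analysis.

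**The concern.** Averaging ratios with equal weight gives a patient seen for one month the same influence as a patient seen for two years, although the one-month rate is far noisier. Because the time is in the denominator, a single relapse before an early exit becomes a very large annual rate. This is a single-arm study with one primary number, so a few such patients could set it.

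The conflict over missing counts adds a second problem. Depending on which text is programmed, early leavers who relapsed either carry very high leverage or disappear from the primary analysis, and these two outcomes push the estimate in opposite directions.

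The plan already handles this differently elsewhere. SAP 15.1 defines adverse event rates as all events over all time on study, which weights patients by exposure.

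**Working it through.** **No figure to reproduce.** The sample size and precision material is redacted, and no expected ARR, SD or dropout rate is visible. Every size below rests on stated assumptions.

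**Inputs from the documents.** The per-patient formula, the equal-weight mean and the normal-theory 95% CI are as described above. For planned follow-up, Protocol 9.2.3 says: "Patients will be followed for 24 months from first dose and up to 30 months".

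**Leverage of one relapse** (365.25 / days on study):
- 30 days: 365.25/30 = 12.18
- 91 days: 365.25/91 = 4.01
- 731 days: 365.25/731 = 0.50

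One day-30 relapser adds 12.18/150 = 0.081 to the mean at N = 150, or 12.18/250 = 0.049 at N = 250. A completer with one relapse adds 0.003 or 0.002.

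**Worked example** (assumed N = 200, 50 patients with one relapse each, everyone else followed 731 days):

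| Scenario | Sum of per-patient rates | Mean (95% CI) | Share of sum from early leavers |
|---|---|---|---|
| All complete | 50 × 0.4997 = 24.98 | 0.125 (0.095–0.155) | none |
| 1 relapser leaves day 30 | 49 × 0.4997 + 12.18 = 36.66 | 0.183 (0.061–0.306) | 33% |
| 3 leave day 30 | 47 × 0.4997 + 36.53 = 60.01 | 0.300 (0.093–0.507) | 61% |
| 3 leave day 91 | 47 × 0.4997 + 12.04 = 35.53 | 0.178 (0.105–0.250) | 34% |

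The pooled rate barely moves. With three day-30 exits, time is (197 × 731 + 3 × 30)/365.25 = 394.5 patient-years, and 50/394.5 = 0.127. With all complete it is 0.125.

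**Simulation, dropout unrelated to relapse.** Assumptions: N = 150 or 250; true ARR 0.1, 0.2 or 0.3; negative binomial dispersion 0, 1 or 2; dropout 0% or 20%, with exits spread uniformly from month 0.25, 1 or 3 up to month 24; 6,000 replicates per setting.
- Planned interval: coverage 93.5–95.0% with no dropout and 91.8–95.1% with 20% dropout (usually 93–94.5%). Most misses lie below the true rate.
- Pooled rate with a robust log-scale interval: 94.0–95.4%.

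**Simulation, exit linked to relapse.** Assumptions: 10% background dropout, plus a share of relapsers leaving the study 30 days after their first relapse; N = 150 or 250; dispersion 0 or 1; 1,500 replicates.

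| Share of relapsers leaving | True ARR | Planned mean | Planned coverage | Mean if leavers are dropped |
|---|---|---|---|---|
| 10% | 0.10 | about 0.12 | about 95% | 0.09 |
| 10% | 0.20 | about 0.235 | 89–95% | 0.19 |
| 25% | 0.10 | about 0.15 | 80–91% | 0.08 |
| 25% | 0.20 | 0.28–0.29 | 53–85% | 0.16 |

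In the 25% setting the planned mean is roughly 40 to 50% high (0.28/0.20 = 1.40; 0.15/0.10 = 1.50). Dropping leavers puts it about 20% low (0.08/0.10 and 0.16/0.20 are both 0.80). Pooled-interval coverage across all these settings was 93.7–95.7%. The pooled rate is not wholly immune: its lowest average was 0.194 for a true 0.20, about 3% low.

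**Do the planned sensitivity analyses close the gap?** The all-reported-relapses analysis is again an unweighted mean. Its time is capped from above but has no floor, so a day-30 exit keeps its leverage. The main negative binomial model takes the same missing-data handling as the primary, so it inherits the same uncertainty about who contributes.

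**The case against.** The strongest reply is that the day-30 relapser may never enter the primary mean. That patient has no Month 12 visit, so under the text below the SAP 14.1.1 table and SAP 14.1.4 the ARR is missing. This stands as a possible reading. It does not clear the plan: the handling column says the opposite, and dropping such patients biases the estimate the other way.

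A reader might infer that the planned interval under-covers as a matter of course. The documents do not support that. With dropout unrelated to relapse the shortfall is between nothing and about 3 points. Where coverage collapses, the main cause is bias in the estimate, not the normal approximation.

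A reader might also infer that the estimate is biased upward because patients leave or switch after a relapse. Nothing in the documents says how often relapse leads to study exit. Stopping or switching treatment does not end follow-up under Protocol 9.2.3; only leaving the study shortens the time. Even the direction of bias depends on which missing-data rule is applied.

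The plan also has safeguards. The primary table shows the SD, quartiles and maximum, so an outlying rate would be visible. Negative binomial models, completer and dropout subgroups and possible multiple imputation are planned. These would help a careful reader notice the problem, but none of them specifies an overall exposure-weighted rate.

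**Conclusion.** The concern holds in a limited form. The primary estimator gives equal weight to rates of very unequal precision. Under the handling stated in the SAP 14.1.1 table, one to three relapsers who leave by day 30 can supply a third to more than half of the estimate in the 200-patient example. That leverage follows from the formula. Its size in this study depends on N, the relapse rate and the timing of exits, none of which is visible.

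Material bias and under-coverage are conditional on exit that follows relapse. In the assumed 25% scenario the result is roughly 40 to 50% high or about 20% low, according to which of the conflicting rules is programmed. The conflict is therefore as important as the choice of estimator and must be settled first. Promoting the negative binomial model alone would leave it in place.

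**What to change.** 1. Reconcile the handling column and the missing-count text of SAP 14.1.1 with SAP 14.1.2 and 14.1.4. Each patient's relapse count and time at risk should cover the same observed period, and early leavers should contribute both. Apply the same rule to the negative binomial models.
2. Make the primary estimate an overall exposure-weighted rate: total relapses divided by total patient-years, with a robust log-scale 95% CI. An intercept-only negative binomial model with a log-time offset is an acceptable alternative. Keep the mean of per-patient ARRs as a descriptive line.
3. Record the change in SAP section 7. A pooled rate fits Protocol 9.7.3, which asks only for an ARR with a 95% CI. A negative binomial primary departs from it, because the protocol calls that model a sensitivity analysis.
4. If the database is already locked, report the pooled rate beside the planned mean and identify it as added, as SAP section 4 requires for unplanned analyses. SAP version 4.0 is dated 23 January 2025, after the planned last patient visit of 3 January 2025 and before the planned lock of 17 February 2025.

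The cost is a documented change of primary estimator and a small amount of programming, since the overall rate is not among the outputs now specified. No new data are needed.
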